2.3 RISK/BENEFIT ASSESSMENT

2.3.1 KNOWN POTENTIAL RISKS

2.4 POTENTIAL RISKS

Endoscopy, EUS, and ePFT: Upper GI endoscopy (EGD) and endoscopic ultrasound (EUS) are routine clinical diagnostic procedures that are typically performed under conscious sedation or monitored anesthesia care. Diagnostic EGD and EUS have a low (< 1%) risk of risk of complications, including reactions to medications given for sedation, bleeding, infection, pancreatitis, perforation, or urgent surgery for complications. All study participants will be undergoing a baseline clinically indicated EGD or EUS exam as well as a subsequent research EGD exam, with endoscopic pancreatic function tests (ePFTs) during both exams.

ePFT is performed during EGD and EUS and involves administration of intravenous secretin. ePFT lengthens the duration of an endoscopic exam because pancreas juice is collected from the duodenum via the endoscope for 45 minutes after secretin administration. There is no evidence that performance of ePFT increases the overall risks of EGD or EUS.

Side effects of intravenous secretin administration occur in < 1% and include diaphoresis, hypotension, nausea, abdominal pain, vomiting, mild pancreatitis, upset stomach, diarrhea, flushing, and a warm sensation in the abdomen. Acute pancreatitis was observed after intravenous secretin administration during MRI in 2/10,000 patients (0.02%).²¹ Contraindications to secretin administration include known hypersensitivity to secretin. Secretin is commonly administered to patients with a history of prior acute pancreatitis or chronic pancreatitis, and there is no evidence that risks are increased in these patient populations. The secretin administered in this study is a recombinant protein identical to human secretin, thus risks of allergic reactions are very low.

Indomethacin (IN) is a nonsteroidal anti-inflammatory drug (NSAID), and many drugs in this class are available over-the-counter. IN was chosen for use in this protocol because rectally administered IN is known to have a beneficial anti-inflammatory effect in human pancreas for prevention of post-ERCP pancreatitis. Like other NSAIDs, IN has a low risk of complications, including allergic reactions, gastrointestinal ulceration, GI bleeding, and a small increased risk of vascular events such as stroke or myocardial infarction. Patients with a history of allergy to NSAIDS, current or past gastroduodenal ulceration, or past history of stroke, myocardial infarction, or coronary artery disease are excluded from participation in this study.

Alternative approaches and treatments: The study protocol utilizes the least invasive, least risky method of assessing human pancreatic COX-2 activity at baseline and after drug treatment.

There are no effective medical therapies for CP that alter the natural history of the disease. Study participants will be patients with CP who will be receiving concurrent care for their condition as clinically appropriate and as determined by their treating physician.

Women who are pregnant or nursing: Risks of endoscopy and sedation may be increased in women who are pregnant or nursing, and they are excluded from participation in this study.

Women of child-bearing potential will undergo a urine pregnancy test within 48 hours of their research EGD exam. In addition, at the time of enrollment (as detailed in the ICF) they must agree to one of the following birth control methods:

- Hormonal methods, such as birth control pills, patches, injections, vaginal ring, or implants
- Barrier methods (such as a condom or diaphragm) used with a spermicide (a foam, cream, or gel that kills sperm)
- Intrauterine device (IUD)
- Abstinence (no sex)

They must use birth control for the entire study and for at least 5 days after their last dose of study drug.

Psychological, legal and financial risks: Study questionnaires will collect confidential information, including medical history, medications used, pain ratings, and quality of life information. Public release of this information might have adverse consequences for study participants. All study data will therefore be stored in secure paper files or de-identified, password-protected electronic databases.

Protections Against Risk

Endoscopic procedures will be performed on clinical GI Endoscopy Units at the current standard of clinical care at Mayo Clinic Rochester and Ohio State University, including the use of monitored anesthesia care (MAC) or general anesthesia (GA) at the discretion of the attending gastroenterologist and anesthesiologist. Participants will receive pre-procedure evaluation, intra-procedural monitoring, and post-procedural recovery care identical to that provided to patients undergoing endoscopy in these units. Staff nurses, anesthetists, and GI endoscopists will be available to assess symptoms and adverse events and provide appropriate treatment during endoscopic procedures and their recovery period. Participants will be discharged from the endoscopy unit when they meet the unit's standard discharge criteria.

Subjects with a history of gastroduodenal ulceration, GI bleeding, stroke, myocardial infarction, or currently active acute pancreatitis are excluded from participation. Subjects found to have active gastric or duodenal ulceration at the time of baseline endoscopy are also excluded. Women who are pregnant or nursing and persons older than 70 years of age, who are at higher risk for aspirin or NSAID-related adverse events, are also excluded from this study.

Women of child-bearing potential (i.e., women who are pre-menopausal and have not had a hysterectomy) must have a negative urine pregnancy test within 48 hours of initiating study drug treatment, and must agree to remain sexually abstinent or use birth control measures (as detailed above) for the duration of their study participation and for 5 days afterward.

Subjects will be contacted weekly by telephone by a study coordinator during their 4 weeks of study drug administration. The coordinator will ask about compliance with study medication, completion of the daily symptom and medication diary, and new or worsening symptoms or

health concerns. Subjects will be encouraged to report new symptoms or health problems to study staff, which will result in communication between a physician-investigator and the subject. Subjects will be able to report symptoms or ask questions at other times by telephone. A study physician will be available to respond to subjects by telephone at all times.

Study enrollment logs containing individually identifiable private information will be stored in secure non-public sites at each study site, as detailed above.

Incidental findings noted during study endoscopy will be described in the clinical endoscopy report generated after each endoscopy exam, which is placed in the patient's medical record. Subjects will be informed of incidental findings and encouraged to follow-up with their clinical care professional about any incidental findings.

2.4.1 KNOWN POTENTIAL BENEFITS

Subjects are unlikely to benefit from participation in this study. If indomethacin suppresses pancreatic PGE₂ production it may improve symptoms and delay progression of CP, but this would probably require long-term administration. On the basis of knowledge gained by this study there is substantial potential benefit to future patients with CP. The risks of study participation are low, and the potential benefit to future patients justifies the risks undertaken by subjects in this study.

2.4.2 ASSESSMENT OF POTENTIAL RISKS AND BENEFITS

Potential risks and benefits, and adequacy of protection against risks, are described in the proceeding sections. There are currently no effective medical therapies for CP, and there is promising background and preliminary data to suggest that NSAIDs may be such a therapy, suggesting that there is significant potential for future benefit of CP patients. The overall risks to subjects are low, and are outweighed by the potential benefits.

3 OBJECTIVES AND ENDPOINTS

OBJECTIVES	ENDPOINTS	JUSTIFICATION FOR ENDPOINTS
Primary		
Primary Objective: to assess the physiologic effect of orally administered indomethacin (IN) on pancreatic juice PGE ₂ concentrations in patients with chronic pancreatitis (CP).	Primary Endpoint: Decrease in mean pancreatic juice PGE ₂ concentration after indomethacin treatment, to no more than 66% of baseline, and statistically significant in comparison to placebo.	Physiologic endpoint that would justify future large-scale clinical trials of IN in CP with primary endpoints related to patient-reported outcomes.
Secondary/Exploratory		

OBJECTIVES	ENDPOINTS	JUSTIFICATION FOR ENDPOINTS

Secondary Objectives:
 
A) To correlate drug-induced changes in pancreatic juice PGE₂ levels with changes in salivary and blood PGE₂ levels, blood IN levels, and changes in patient-reported pain outcome (PRO) and quality of life (QOL).
	
Secondary Endpoints: Correlation of pancreatic juice, blood, and saliva PGE₂ levels; correlation of post-treatment decreases in pancreas juice PGE₂ concentrations with improvements in patient-reported outcomes (pain and quality of life); explore changes in cytokine, microbiome and pancreas function with IN administration
	
Provide further insight into the pancreatic effects of IN, determine whether measurement of PGE₂ in fluids collected noninvasively correlate with pancreatic juice PGE₂ concentrations, and provide pilot data regarding PRO and QOL outcomes useful for planning subsequent clinical trials.

4 STUDY DESIGN

4.1 OVERALL DESIGN

This is a phase 1 / 2, randomized, placebo-controlled, double-blinded study of oral indomethacin 50 mg po BID vs. placebo po BID in patients with chronic pancreatitis. The study will be conducted at Mayo Clinic Rochester and Ohio State University.

The study **hypothesis** is:

- 1) That mean pancreatic juice PGE₂ concentration will decrease after indomethacin treatment to no more than 66% of baseline, and will be significantly lower than after placebo treatment.

[figure not shown]
Exploratory hypotheses are:

- 1) That peak blood IN levels at the conclusion of treatment will correlate with degree of change in pancreas juice (PJ) PGE₂ concentrations.
- 2) That baseline salivary and blood PGE₂ concentrations, and changes in these concentrations after treatment, will correlate with blood and saliva PJ PGE₂ concentrations.
- 3) That improvement in pain and quality of life of study participants will correlate with changes in PJ PGE₂ concentrations.

Overview: 32 participants with CP will be randomized to receive 28 days of IN 50 mg po BID or placebo (2 study arms). Blood, saliva, and pancreatic juice will be collected from each participant prior to study drug administration and again on the 28th day of study drug administration. Participants will complete daily pain diaries as well as questionnaires assessing pain and quality of life at baseline and day 28. Primary outcome is a comparison of the mean change in PJ PGE₂ concentrations at 28 days in the IN vs. placebo groups. Secondary outcomes include changes in

pain and quality of life from baseline to 28 days in the IN vs. placebo groups, and their correlation with changes in PJ PGE₂ and blood IN concentrations, as well as correlation of PJ, saliva, and blood PGE₂ concentrations (to determine whether non-invasive measures correlate with PJ measures).

Methods: Up to 40 participants will be enrolled in order to accrue 32 participants who complete the study protocol. As shown in **Figure 3**, all study participants will undergo a biospecimen collection at baseline and day 28 including blood, saliva, and pancreatic juice (PJ). PJ will be collected during endoscopic pancreatic function tests (ePFT). Up to 4 weeks may elapse between the baseline biospecimen collection and day 1 of study drug administration. 16 participants will receive oral indomethacin 50 mg BID, and 16 will receive matched placebo BID. Participants will complete the Brief Pain Inventory (BPI) and PROMIS 10 quality of life instrument at baseline and day 28, and will also complete daily symptom and medication diaries.

Definitions: CP will be diagnosed per American Pancreatic Association criteria for definite CP. These include a compatible clinical picture with definite findings of CP (Cambridge 3-4 ductal changes, and/or calcifications) on cross-sectional imaging studies.

Study Interventions and Measures: The *endoscopic pancreatic function test (ePFT)* will be performed at baseline and on day 28. ePFT is a standardized test used in medical pancreatology clinical practice that involves administration of intravenous secretin (0.2 mcg/kg slowly over one minute) to stimulate pancreatic juice secretion, followed by aspiration of pancreatic juice from the duodenum via an endoscope. Some subjects will undergo a baseline ePFT as part of their routine clinical care; other subjects, who are having upper GI endoscopy or endoscopic ultrasound (EUS) performed as part of their clinical care, will undergo ePFT during endoscopy for research purposes. Fluid will be aspirated from the duodenum via an endoscope at baseline and from 0-10 and 10-20 minutes following secretin administration, and processed per CPDPC pancreas juice/fluid SOP. Participants will be instructed to take their study drug 2 hours prior to their follow-up research endoscopy with ePFT on day 28.

PJ bicarbonate and lipase concentrations will be measured on duodenal aspirates from each time point using a previously validated method. ¹⁸ *PGE₂ concentrations* will be measured in saliva, blood, and pancreatic juice from baseline and day 28 using a tandem mass spectroscopy assay developed and validated at Mayo Clinic Rochester. *Peak IN drug levels* will be measured in blood on day 28, providing an assessment of participant compliance with study drug administration.

The *Brief Pain Inventory (BPI)* and the *PROMIS-10* are validated scales that quantify pain and quality of life, respectively, and will be completed at baseline and day 28. A *medication and pain diary* will be completed daily by all subjects at baseline and during the 28-day treatment period,

including all narcotics and over-the-counter medications used. Oral opioid usage will be expressed in oral morphine equivalents for purposes of data analysis.

Randomization, Allocation and Blinding

Randomization: Subjects will be assigned to receive IN or placebo according to a computer generated randomization list composed of randomized blocks of sizes of 2 or 4. Two separate sets of blocks will be created, one for subjects with alcoholic CP and the other for those with other causes of CP. Within each block, equal number of subjects will be assigned to IN and placebo. Separate sets of randomization blocks will be provided for Mayo and Ohio State. The randomization lists will be computer generated by the study statistician ([name]), and kept in a secure computer file and paper study binder in the Mayo and Ohio State Research Pharmacies. No investigators or study personnel other than [name] will have knowledge of the randomization list. [name] will not participate in any aspect of subject recruitment, subject allocation, conduct of the study, or data ascertainment, but will perform data analysis.

Subject allocation will be known only to the staff of the Mayo and Ohio State Research Pharmacies, who will assign subjects to IN or placebo according to their randomization list provided by [name]. Allocation will be performed by matching the subject's study number with the randomization list. Allocation will not be revealed to subjects, investigators, other study personnel, or clinicians caring for subjects until all subjects have completed the clinical trial or for medical emergency. Because subjects, investigators, and study personnel will be blinded, they will not be able to determine subject allocation before or during data ascertainment.

In case a subject is allocated to receive study medication, but is withdrawn from the study before completing the protocol, study medication will be returned to the Research Pharmacy for disposal, and the following subject will be assigned the same allocation. All investigators will remain blinded to the allocation of the withdrawn subjects and their replacements.

Blinding: Study medication will be labelled "indomethacin 50 mg or placebo capsule" with the subject's name, hospital or clinic number, study IRB number, and subject number. Placebo and IN capsules will be identical in appearance. The investigators, study coordinator, and clinical caregivers will remain blinded to subject allocation throughout the data ascertainment and data entry phase of the study.

The success of blinding will be evaluated by asking the investigator, the study coordinator, and the subject the following question during their final study visit: "Which treatment group is this subject/were you assigned to: placebo, active drug, or unsure?"

Statistical Analysis and Sample Size

For Specific Aim 1, the primary analysis will be a linear random intercept model that incorporates PJ PGE₂ data from both baseline and day 28 from all randomized patients. Transformation will be used as appropriate to reduce the skewness of data and satisfy modeling assumption. The model includes randomized groups, time, and their interactions as fixed effect covariates, from which the mean change in PJ PGE₂ will be estimated for each randomized group. Effects of additional covariates, such as sex and sites, will be explored. The intra-subject correlation will be

estimated from the variances of the random intercepts and residuals. Other outcome variables, such as other biomarkers and questionnaire data, can be analyzed in a similar way. The estimates about the variability of data and intrasubject correlations will be useful for designing a subsequent larger study.

For Specific Aim 2, we will use multivariate analysis of variance model (MANOVA) with repeated measures. The multivariate outcomes include patient-related outcomes (BPI and PROMIS-10 scores) and PJ PGE₂ concentrations at baseline and day 28. Fixed effect covariates include randomized groups, time, and their interactions. Additional secondary analyses include descriptive analysis and statistical comparison of PJ PGE₂ concentrations at baseline and after secretin administration between the various study groups, and correlations between baseline PJ PGE₂ levels, clinical features, and changes in plasma and saliva PGE₂ levels. Changes in daily pain ratings and narcotic use (in morphine equivalents) will be analyzed in comparison to changes in PJ PGE₂ concentrations. Any dropout before Day 28 will be documented and descriptively summarized. Sensitivity analysis on dropout will be conducted in an exploratory manner according to standard missing data analysis procedure for longitudinal data.¹⁹ As a pilot study, we will collect and descriptively analyze data on feasibility, patient compliance and satisfaction, and attrition, in order to inform the possible future study.

We propose a sample size of 16 patients per treatment arm. Since this is a pilot study, this sample size is largely limited by budgetary restraint. However, this sample size is adequate for studying the primary hypothesis with a two-sample two-sided t-test on the mean PGE₂ level at day 28 between the randomized groups. We expect to show that the treatment group has significantly lower mean PGE₂ than the placebo group. In our previous publication on PJ PGE₂,²⁰ we reported that median PJ PGE₂ level in 10 CP patients was 307 pg/ml with IQR of 249-362 pg/ml and standard deviation of 84 pg/ml. The boxplot of that data suggests that normality is a reasonable distributional assumption for the PGE₂ data. That study also found that mean PJ PGE₂ in a healthy control group was 104 pg/ml, about one third of the mean level of the CP group. If we conservatively assume that the control group in the proposed trial has 50% decrease in mean, with a Type I error of 0.05, the power of the t-test is 0.998. If we use an even more conservative mean for the control group, with 1/3 reduction in mean PGE₂, the power is 0.94. If we additionally assume that there is some data loss (due to consent withdrawal, dropout, or specimen mishandling) so that the sample size per treatment group is 12 instead of 16, the statistical power decreases to 0.85, but is still reasonable. Note that the large statistical power in the calculation above is a result of the relatively small standard deviation of the PGE₂ compared with our working assumption on the mean reduction. This assumption is supported by the data in Abu Dayyeh et al.²⁰ If this pilot study is successful, demonstrating a statistically significant indomethacin-related decrease in PJ PGE₂ by at least 1/3, we will conduct a future study that focuses on patient centered outcomes; that study is expected to have a larger sample size because those outcomes are expected to be less sensitive to the treatment than biomarkers. Only if indomethacin treatment achieves this result would longer-term trials of indomethacin at this dose be warranted. The data from this pilot study will provide critical preliminary and feasibility data for the future investigation.

Timeline and Feasibility: Both Mayo Clinic Rochester (MCR) and Ohio State University (OSU) medical centers feature busy medical pancreatology practices. Average monthly new patient

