6.3 MEASURES TO MINIMIZE BIAS: RANDOMIZATION AND BLINDING

Randomization: Subjects will be assigned to receive IN or placebo according to a computer generated randomization list composed of randomized blocks of sizes of 2 or 4. Two separate sets of blocks will be created, one for subjects with alcoholic CP and the other for those with other causes of CP. Within each block, equal number of subjects will be assigned to IN and placebo. Separate sets of blocks will be provided for Mayo and Ohio State. The randomization lists will be computer generated by the study statistician ([name]), and kept in a secure computer file and paper study binder in the Mayo and Ohio State Research Pharmacies. No investigators or study personnel other than [name] and staff at Mayo/OSU research pharmacies will have knowledge of the randomization list. [name] will not participate in any aspect of subject recruitment, subject allocation, conduct of the study, or data ascertainment, but will perform data analysis with de-identified data.

Subject allocation will be known only to the staff of the Mayo and Ohio State Research Pharmacies, who will assign subjects to IN or placebo according to their randomization list provided by [name]. Allocation will be performed by matching the subject's study number with the randomization list. Allocation will not be revealed to subjects, investigators, other study personnel, or clinicians caring for subjects until all subjects have completed the clinical trial or for medical emergency. Because subjects, investigators, and study personnel will be blinded, they will not be able to determine subject allocation before or during data ascertainment.

Allocation will be performed on the day of the participant's baseline endoscopy with pancreas juice collection. One container of study medication containing 28 days of medication (56 capsules) will be dispensed to the participant that day.

In case a subject is allocated to receive study medication, but is withdrawn from the study before completing the protocol, study medication will be returned to the Research Pharmacy for disposal.

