7.2 PARTICIPANT DISCONTINUATION/WITHDRAWAL FROM THE STUDY

Participants are free to withdraw from participation at any time upon request. An investigator may withdraw a participant from the study for the following reasons:

1. Found to have active gastrointestinal ulceration at the time of their baseline, clinically indicated GI endoscopy procedure.
2. Positive pregnancy test in a woman of child bearing potential.
3. Significant study medication non-compliance (defined as failure to take at least 66% of study medication doses, as determined during telephone follow-up calls).
4. Hospitalized for acute pancreatitis during study participation.
5. Other acute illness that requires breaking study blinding and discontinuing study medication for clinical reasons.

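### A withdrawn subject's arm passes to the next subject, so an unblinded withdrawal reveals the next allocation before it is made

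*Combined protocol and SAP*

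**What the plan says.** Section 4.1, under randomization, allocation and blinding, describes computer-generated lists in blocks of 2 or 4, balanced within block. There are separate lists by cause of pancreatitis (alcoholic or other) and by site, so four in all. The research pharmacies assign treatment: "Allocation will be performed by matching the subject's study number with the randomization list".

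For a subject who has been allocated and is then withdrawn early, 4.1 says that "the following subject will be assigned the same allocation", and adds: "All investigators will remain blinded to the allocation of the withdrawn subjects and their replacements". The same section keeps allocation concealed "until all subjects have completed the clinical trial or for medical emergency".

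Section 7.2 lists reasons for which an investigator may withdraw a participant. Item 5 is "Other acute illness that requires breaking study blinding and discontinuing study medication for clinical reasons".

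Section 6.3 repeats most of the 4.1 text, including study-number matching and the site lists ("Separate sets of blocks will be provided for Mayo and Ohio State"). Its paragraph on withdrawn subjects ends with "study medication will be returned to the Research Pharmacy for disposal" and has no replacement rule. It also fixes the timing: "Allocation will be performed on the day of the participant's baseline endoscopy with pancreas juice collection".

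**The concern.** Concealment requires that nobody who can influence who is randomized next, or when, knows the next arm. The rule in 4.1 links the next arm to a past one. That is harmless only as long as the past one stays secret, and the plan itself provides for cases in which it does not.

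There is also an operational problem. The pharmacies have two accounts of what to do after a withdrawal, one with the rule and one without. Neither explains how an inherited arm fits with looking up a study number on a list.

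In a trial of 32 completers, even one or two steered assignments are a visible share of an arm. Nothing in the analysis can detect or repair them.

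**Working it through.** **1. The passages side by side.**
- Withdrawal under 7.2 item 5 requires the blind to be broken, and 4.1 allows this in a medical emergency.
- The rule in 4.1 then gives the next subject the arm just disclosed.
- The blinding promise in 4.1 covers withdrawn subjects and their replacements without exception. Both statements could hold only if the disclosure never reached an investigator, and I found no unblinding procedure that confines it in that way.
- 6.3 is silent on replacement. Both sections allocate by matching the study number to the list, which does not describe inheritance.

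**2. How many allocations could be inherited.** Section 4.1 sets a ceiling of 40 enrolled to reach 32 completers: 40 − 32 = 8, and 8/40 = 20%. This is an upper limit on inherited arms. The number of those that follow an unblinding is not given anywhere and could be anything from 0 to 8.

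**3. Predictability with and without the rule.** Suppose one allocation on a list becomes known.
- Under the rule, the next arm is known with probability 1.00.
- Under list order, assume blocks of 2 and 4 are used equally often. Then 1/3 of entries lie in blocks of 2 and 2/3 in blocks of 4. Two entries have the same arm with probability 0 within a block of 2, 1/3 within a block of 4, and 1/2 across blocks.
- Adjacent entry: P(same) = (1/3)(½·0 + ½·½) + (2/3)(¾·⅓ + ¼·½) = 0.083 + 0.250 = 0.333. The best guess is right with probability 0.67. Simulation gave 0.672.
- Two entries on: 0.56. Four or more: 0.50.

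**4. Possible bias (illustration, assumed inputs).** Suppose k foreknown allocations are each steered by b SD of PGE₂, always in the same direction for the treatment contrast. With SD 84 and 16 per arm, the difference shifts by k × b × 84/16 pg/ml.
- k = 1, b = 0.25 to 1: 1.3 to 5.25 pg/ml.
- k = 8, b = 0.25 to 1: 10.5 to 42 pg/ml.
- The planned one-third reduction is 307/3 = 102.3 pg/ml.

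**5. Arm sizes.** Permuted blocks were simulated in four equal strata, 4,000 trials per setting, with inheritance kept within stratum and dropout rates assumed. Mean absolute difference between arms:

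| Dropout, placebo / indomethacin | Rule | Randomized set | Completers |
|---|---|---|---|
| 20% / 20% | yes | 2.9 | 1.3 |
| 20% / 20% | no | 1.3 | 2.3 |
| 10% / 30% | yes | 4.8 | 1.3 |
| 10% / 30% | no | 1.2 | 4.1 |

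The rule balances completers and unbalances the randomized set, which is the set 9.4.2 names for the primary model.

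**6. What the rule buys in power.** The inputs from section 9.2 are mean 307, SD 84, a one-third reduction and two-sided 0.05. The plan's own figures come first. The noncentrality at 16/16 is 102.3/(84·√(1/16 + 1/16)) = 3.446. The normal approximation gives Φ(3.446 − 1.960) = 0.931 against the stated 0.94. It gives 0.847 against 0.85 at 12 per arm, and 0.999 against 0.998 for a 50% reduction. The noncentral t (30 df) is slightly lower:

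| Split of 32 | Noncentrality | Power (t) |
|---|---|---|
| 16/16 | 3.446 | 0.915 |
| 17/15 | 3.439 | 0.914 |
| 18/14 | 3.419 | 0.911 |
| 20/12 | 3.336 | 0.898 |

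**The case against.** The strongest reply is that an inherited arm was itself drawn at random and is known only to the pharmacy staff and the statistician. With the blind intact, an investigator can predict it no better than a fresh entry. This stands. A reader might infer that replacements are not randomized, or that concealment fails for 20% of subjects. The documents support neither: the 8 of 40 counts inherited arms, not foreknown ones. Even that ceiling is loose, because losses before allocation (a creatinine result out of range, for example) use up places without triggering the rule.

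Three further limits also stand.
- Of the grounds listed in 7.2, only item 5 by its terms involves unblinding. A withdrawal for side effects may prompt a guess, which the rule would carry forward, but a guess is not knowledge.
- Consent can precede allocation by up to 28 days. The exposure is therefore before randomization, and not necessarily before the decision to enrol.
- A reader might infer that the rule breaks the stratified blocks. That is one reading. The pharmacies may well take the wording to mean the next subject on the same list, which would preserve the strata. The text does not say.

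It can also be said that, with the blind intact, treatment-related withdrawal changes how many subjects enter each arm and not which ones. That is correct. The imbalance in step 5 is a matter of arm sizes and is not in itself a bias.

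None of this answers the narrow case. After an item 5 withdrawal the next arm is certain to anyone told of it, and 4.1 promises otherwise.

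**Conclusion.** The point holds in a limited form. The rule makes a replacement's arm dependent on the withdrawn subject's. After an unblinded withdrawal it turns that dependence into certain foreknowledge, in conflict with the blinding promise in 4.1. Sections 4.1 and 6.3 disagree on whether the rule exists, and its scope across lists is undefined.

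The likely size is small. There are at most 8 inherited arms, an unknown and probably small number of them foreknown, and an illustrative shift of about 1 to 5 pg/ml per steered subject against 102. That range rests on an assumed 0.25 to 1 SD of steering. The imbalance figures rest on assumed dropout rates and equal strata. The correction is worth making because it is cheap and the rule gains almost nothing, not because the trial's result is in doubt.

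**What to change.** Delete the same-allocation sentence in 4.1 so that it agrees with 6.3. State in both sections that every new participant, including one enrolled after a withdrawal, receives the next unused entry on the list for his or her own site and etiology, within the ceiling of 40. Carry the same wording into the pharmacy instructions and prepare each list long enough. Withdrawn participants stay in the randomized set, as 9.4.2 already provides. The completer and per-protocol wording in 9.3 has to be reconciled with that separately.

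The cost is wording plus some possible imbalance among completers: 0.4 points of power at 18/14 and 1.8 points at 20/12 (0.915 − 0.898 = 0.017 from the rounded values; 0.9152 − 0.8976 = 0.0176 unrounded). With equal 20% dropout, a difference of 4 or more among completers occurred in about 26% of simulated trials without the rule, against 5% with it. With 10% and 30% dropout, a difference of 8 or more occurred in about 11% without the rule.

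The change reduces predictability but does not remove it. With blocks of 2 or 4, one unblinded allocation still predicts an adjacent entry with probability about 0.67.
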